2. SUMMARY OF KEY PROTOCOL INFORMATION

2.1. Changes to the Protocol Defined Statistical Analysis Plan

Statistical analysis changes to the originally planned statistical analysis specified in the protocol amendment 1 (Dated: 23-MAR-2016) (GSK Document No.: [2015N243304_01](#)) are outlined in [Table 1](#).

Table 1 Changes to Protocol Defined Statistical Analysis Plan

Protocol	Reporting & Analysis Plan	Rational for Changes
Statistical Analysis Plan	Statistical Analysis Plan	

 Analysis of change from baseline in ACQ, SQRQ scores will be performed using a mixed models repeated measures (MMRM) analysis, allowing for covariates of baseline ACQ score, region, baseline maintenance OCS therapy, exacerbations in the year prior to the study (as an ordinal variable), visit and an interaction term for visit by baseline ACQ score. Clinically significant exacerbations will be analyzed using a generalized linear model with covariates for region, baseline maintenance OCS therapy and number of exacerbations in the year prior to the study (as an ordinal variable). 	
 Baseline values will be included as a data point in the analysis, and there will be no covariate adjustment made in the model. The change from the baseline at Visit X will be calculated by: Estimated Score at Visit X minus Estimated Score at Baseline. Clinically significant exacerbations will be examined using a generalized estimating equation (GEE) with no adjustments for covariates. 	
 This is a single treatment arm study and comparisons are being made directly to the baseline values. Generalised estimating equations (GEEs) will compare the on-treatment exacerbation rate to the rate within the 12 months prior to study.

[figure not shown]

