8. SECONDARY STATISTICAL ANALYSES

8.1 Efficacy Analyses

8.1.1. Overview of Planned Efficacy Analyses

The secondary efficacy analyses will be based on the Intent-To-Treat (ITT) population, unless otherwise specified in [Appendix 13: List of Data Displays](#).

[Table 5](#) provides an overview of the planned efficacy analyses, with further details of data displays being presented in [Appendix 13: List of Data Displays](#).

Table 5 Overview of Planned Efficacy Analyses

Endpoint	Absolute ^[1]						Change from Baseline ^{[1] [2]}						
	Stats Analysis			Summary		Individual	Stats Analysis			Summary		Individual	
	T	F	L	T	F	F	L	T	F	L	T	F	F
Secondary Endpoints													
St George's Respiratory Questionnaire (SGRQ)													
On-treatment & Off-treatment	Y			Y				Y	Y		Y	Y	
Blood Eosinophil Count													
On-treatment & Off-treatment	Y			Y				Y	Y		Y		
On-treatment ^[3]	Y							Y					
Other Endpoints													
>= 0.5-point reduction from baseline in ACQ-5 score at Week 32													
On-treatment & Off-treatment										Y	Y		
>= 4-point or greater reduction from baseline in SGRQ Total score at Week 32													
On-treatment & Off-treatment										Y	Y		
Pre-Bronchodilator FEV1													
On-treatment & Off-treatment	Y			Y				Y	Y		Y		
Post-Bronchodilator FEV1													
On-treatment & Off-treatment	Y			Y				Y	Y		Y		
Subject/Clinician Rated Response to Therapy													
On-treatment ^[3]				Y									
Treatment Satisfaction Questionnaire for Medication (TSQM-9)													
On-treatment ^[3]				Y						Y			
Biomarkers													
On-treatment				Y						Y			

Endpoint	Incidence of Events						
	Stats Analysis			Summary		Individual	
	T	F	L	T	F	F	L
Secondary Endpoints							
Clinically Significant Exacerbations							
On-treatment & Off-treatment	Y ^[4]			Y	Y		Y
On-treatment ^[3]	Y ^[4]						
Exacerbations requiring ED visit/hospitalization							
On-treatment & Off-treatment	Y ^[4]			Y			Y
On-treatment ^[3]	Y ^[4]						
Exacerbations requiring hospitalization							
On-treatment & Off-treatment	Y ^[4]			Y			Y

NOTES :

- T = Table, F = Figure, L = Listing, Y = Yes display generated.
- Stats Analysis = Represents TFL related to any formal statistical analyses (i.e. modelling) conducted.
- Summary = Represents TFL related to any summaries (i.e. descriptive statistics) of the observed raw data.
- Individual = Represents FL related to any displays of individual subject observed raw data.

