1. Absolute and change from baseline summaries combined into a single display.
2. Ratio to Baseline to be shown for Blood Eosinophil Count and Biomarker data.
3. To analyse data collected whilst On-Treatment, not considering any data collected following treatment discontinuation (see Section 10.4).
4. Table to include annualised exacerbation rate and 95% confidence intervals from negative binomial model.

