
 The frequency of clinically significant exacerbations will be analysed using Negative Binomial regression via generalised estimating equations with a covariate of time period (pre-, post-mepolizumab). Exacerbations separated by less than 7 days will be treated as a continuation of the same exacerbation. The pre-mepolizumab exacerbation values (in the 12 months prior) will be obtained at screening, while the post-mepolizumab exacerbation values will be observed during the study. The variance of the mean estimate will be corrected for within-subject correlation. The logarithm of time on treatment will be used as an offset variable.
Model Checking & Diagnostics

 Refer to Appendix 11: Model Checking and Diagnostics for Statistical Analyses.

Secondary Statistical Analyses
Model Results Presentation

 Adjusted exacerbation rate and the corresponding 95% confidence interval will be presented.
On-treatment Phase

 All subjects in the ITT population will be included within this analysis. All data collected up to and including Week 32 from patients, including those who have discontinued study treatment, will be included in the analysis. An On-Treatment “de jure” analysis will also be performed which does not consider any data collected following treatment discontinuation (see On-Treatment definition within Section 10.4).
Sensitivity and Supportive Statistical Analyses

 The On-Treatment “de jure” analysis will be also performed with a subset of patients who were on omalizumab for more than 12 months.

Secondary Statistical Analyses
Secondary Endpoint(s)

 Ratio to baseline in blood eosinophil count at week 32
Model Specification

 See Primary Efficacy Statistical Analysis, Section 7.1.2 A log-transformation will be applied to blood eosinophil count data prior to analysis. If a blood eosinophil count of zero is reported, it will be imputed with half of the lowest possible blood eosinophil count, where applicable, prior to log transforming the data (Note: this imputation has typically been $0.5 * 0.01 \text{ GI/L} = 0.005 \text{ GI/L}$ for previous mepolizumab studies).
Model Checking & Diagnostics

 Refer to Appendix 11: Model Checking and Diagnostics for Statistical Analyses..

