10.4. Appendix 4: Treatment Phases

10.4.1. Treatment Phases (Exacerbations)

Exacerbation data will be classified according to time of occurrence/assessment relative to the first and last date of mepolizumab and the attendance dates of specific visits.

Treatment Phase	Definition
Pre-Treatment	Date & time < First dose of mepolizumab
On-Treatment	Subjects completing treatment and completing the study: First dose of mepolizumab ≤ Date & time ≤ Visit 10 (Exit Visit)* visit date Subjects discontinuing study treatment/withdrawing early from the study: First dose of mepolizumab ≤ Date & time ≤ Earliest of (1) Last dose of mepolizumab + 28 days or (2) Early Withdrawal/Treatment Discontinuation visit date
Off-Treatment	Subjects completing treatment and completing the study: Date & time > Visit 10 (Exit Visit)* visit date Subjects discontinuing study treatment/withdrawing early from the study: Date & time > Earliest of : (1) Last dose of mepolizumab + 28 days or (2) Early Withdrawal/Treatment Discontinuation visit date

* Data may be considered off treatment if beyond acceptable protocol defined limits.

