10.6.4. Safety

Extent of Exposure

- Number of days of exposure to study drug will be calculated based on the formula:
Duration of Exposure in Days = Last mepolizumab dose – (First mepolizumab dose) + 29
- The extent of exposure will also be summarised as the number of study treatments administered

Adverse Events

Adverse Events of Special Interest

Section 8.2.2 provides a full list of AEs of special interest for this compound.

Adverse events of special interest (AESIs) of anaphylaxis reactions, systemic reactions, and local injection site reactions are collected via targeted eCRF. Systemic reactions with preferred terms such as injection related reaction or administration related reaction will be considered non-allergic reactions; those with other preferred terms will be considered allergic/hypersensitivity reactions. The AESIs of opportunistic infections, malignancies, serious CVT events and serious ischemic events will be identified from a list of relevant preferred terms maintained within a project level reference dataset; created based on the latest version of the MedDRA dictionary available at the time of database freeze for this study (See Program Safety Analysis Plan for additional details).

ECG Parameters

RR Interval

All ECG parameters required in this study will be databased, and therefore, further derivations will not be performed by Stats and Programming. The definitions of these parameters are given in this section.

- If RR interval (msec) is not databased, then RR can be derived as :
 - [1] If QTcB is machine read & QTcF is not provided, then :

$$RR = \left[\left(\frac{QT}{QTcB} \right)^2 \right] * 1000$$

- [2] If QTcF is machine read and QTcB is not provided, then:

$$RR = \left[\left(\frac{QT}{QTcF} \right)^3 \right] * 1000$$

- If ECGs are manually read, the RR value should be a collected value and will not be derived.

Corrected QT Intervals

- When not databased, corrected QT intervals by Bazett's (QTcB) and Fredericia's (QTcF) formulas will be calculated, in msec, depending on the availability of other measurements.
- If RR interval (msec) is provided then missing QTcB and/or QTcF will be derived as :

ECG Parameters

$$QTcB = \frac{QT}{\sqrt{\frac{RR}{1000}}}$$

$$QTcF = \frac{QT}{3\sqrt{\frac{RR}{1000}}}$$

- Individual maximum QTc(F) and QTc(B) values will also be summarised by treatment group for each scheduled study visit to show the number of subjects with maximum values (msec) in the following categories:
 - ≤ 450

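### The SAP's pre/post exacerbation model keeps the protocol's one-period offset, log time on treatment, which has no value for the pre-mepolizumab record and does not match the events counted on study

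*SAP*

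**What the plan says.** Protocol 9.4.2 planned a negative binomial model with one on-study record per subject and the logarithm of time on treatment as offset.

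SAP 2.1 (Table 1) replaces this with a comparison against the year before the study: "Generalised estimating equations (GEEs) will compare the on-treatment exacerbation rate to the rate within the 12 months prior to study". SAP 8.1.2 specifies negative binomial regression by GEE with time period (pre, post) as the covariate. On the pre count it says "The pre-mepolizumab exacerbation values (in the 12 months prior) will be obtained at screening". It then repeats the protocol's offset: "The logarithm of time on treatment will be used as an offset variable". It gives no separate denominator for the pre record.

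For the main analysis, SAP 8.1.2 says "All data collected up to and including Week 32 from patients, including those who have discontinued study treatment, will be included in the analysis". SAP 8.1.1 (Table 5) labels that analysis "On-treatment & Off-treatment" and lists an on-treatment analysis separately for clinically significant exacerbations and for those needing an ED visit or hospitalisation. Its note 4 reads "Table to include annualised exacerbation rate and 95% confidence intervals from negative binomial model".

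Three other places bear on the denominator and the window:

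- SAP 10.6.4 has the only formula for time on mepolizumab, under extent of exposure. It begins "Duration of Exposure in Days = Last mepolizumab dose", then subtracts the first dose date and adds 29.
- SAP 10.4.1 bounds the on-treatment phase for subjects who stop early: "First dose of mepolizumab ≤ Date & time ≤ Earliest of (1) Last dose of mepolizumab + 28 days", or the early withdrawal or discontinuation visit. It also defines an off-treatment phase for exacerbations.
- Protocol 7.3.2.4 ends exacerbation collection for early stoppers about 4 weeks after the last dose. Protocol 5.5.1 asks subjects who stop treatment to complete the remaining visits.

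**The concern.** With a log link, the offset is the denominator of the rate, so it must be the time during which the counted events could have occurred. In the protocol's model, time on treatment could serve. In a pre/post model it fails in two ways.

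First, it has no value for half the records. Read literally, the specification cannot be fitted.

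Second, in the main analysis the numerator runs to Week 32 whether or not treatment continues, while the denominator stops with treatment. A subject who stops early and stays in follow-up contributes events from the whole period and time from only part of it. That raises the on-study rate and the post/pre rate ratio.

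The model serves a named secondary endpoint (clinically significant exacerbations) and the ED-or-hospitalisation and hospitalisation-only analyses. The study is open-label and single-arm, so a denominator settled after the data are known would be avoidable discretion.

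**Working it through.** The documents give no planned exacerbation rate or power for this endpoint, so there is no stated figure to reproduce.

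**Pre record.** SAP 2.1 and 8.1.2 both refer to the prior 12 months, and SAP 8.1.1 asks for an annualised rate. A one-year denominator satisfies all three. Time on treatment satisfies none, because it does not exist for that period. Bias with 12 months used: none.

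**Post record: time on treatment.** The exposure formula in SAP 10.6.4 (last dose − first dose + 29) gives:

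| Last dose | Days on treatment | Observed to Week 32 (224 + 1) | Subject's own rate inflated by |
|---|---|---|---|
| Week 28 (completer) | 196 + 29 = 225 | 225 | 1.00 |
| Week 20 | 140 + 29 = 169 | 225 | 225/169 = 1.33 |
| Week 12 | 84 + 29 = 113 | 225 | 225/113 = 1.99 |
| Week 4 | 28 + 29 = 57 | 225 | 225/57 = 3.95 |

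The on-treatment phase in SAP 10.4.1 also ends at last dose + 28 days, or sooner if the early visit comes first. Using it would not lengthen the denominator. Completers are unaffected.

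**Post record: crude person-time.** Let a fraction f stop with d days on treatment, all followed to Week 32, with the same event rate as the others. The overstatement is 225 / [(1 − f)·225 + f·d]. For f = 0.10 and d = 113 this is 225 / (202.5 + 11.3) = 225/213.8 = 1.052.

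**Post record: negative binomial weighting.** The specified model does not weight by person-time. Under an independence working correlation (the SAP names none), the fitted annual rate L solves

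(1 − f)(rT − LT)/(1 + aLT) + f(rT − LS)/(1 + aLS) = 0,

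with T = 225/365.25, S = d/365.25, true rate r and dispersion a. Assumed values are a = 0.5 to 1 and r = 2 to 3 events per year. Stoppers have small fitted means and so get more weight, which makes the overstatement larger than the crude ratio. For f = 0.15, d = 57, a = 1, r = 3, the solution is L = 3.755, and 3.755/3 = 1.25.

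| Fraction stopping | Last dose | Crude | Negative binomial (a 0.5-1, r 2-3) |
|---|---|---|---|
| 5% | Week 20 | 1.013 | 1.01-1.02 |
| 5% | Week 12 | 1.026 | 1.03-1.04 |
| 5% | Week 4 | 1.039 | 1.06-1.08 |
| 10% | Week 20 | 1.026 | 1.03 |
| 10% | Week 12 | 1.052 | 1.06-1.08 |
| 10% | Week 4 | 1.081 | 1.12-1.16 |
| 15% | Week 20 | 1.039 | 1.04-1.05 |
| 15% | Week 12 | 1.081 | 1.10-1.12 |
| 15% | Week 4 | 1.126 | 1.18-1.25 |

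**Simulation check.** This used 120 subjects, 200 runs, 3 events per year, dispersion 0.5, an exchangeable correlation and no true change. With 15% stopping after a random 1 to 7 doses and all followed to Week 32, the mismatched offset gave a rate ratio of 1.13. With 12 months for the pre record and observed time for the post record, it gave 1.00.

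**If Protocol 7.3.2.4 governs.** Counting then stops about 4 weeks after the last dose, numerator and denominator cover nearly the same days, and the overstatement is about zero.

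**The case against.** The best defence is that Protocol 7.3.2.4 is the text specific to exacerbations. SAP Table 1 records no change to that window, and the SAP's reference to all data collected is a stock sentence also used for ACQ-5 and eosinophils. It can be read as limited to what the protocol collects, which leaves almost no mismatch. This stands as a possible reading, and it is why the size can be zero. It does not settle the matter. SAP 8.1.2 expressly includes subjects who have discontinued, SAP 8.1.1 separates the combined analysis from the on-treatment one, SAP 10.4.1 defines an off-treatment phase for exacerbations, and Protocol 5.5.1 plans follow-up after stopping.

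It is also fair that the illustration assumes every stopper is followed to Week 32. The protocol's only attrition figure, 15% in Section 9.2.1, is withdrawal from the study with missing Week 32 data. Such subjects contribute little off-treatment time, so the figures are not forecasts.

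The on-treatment analyses do have a usable matched window in SAP 10.4.1, and setting them beside the main analysis would help expose a mismatch.

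Three stronger readings are tempting, and the documents do not support them:

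- *A spurious benefit.* Giving the pre record the same 224 days as the post record would produce a false ratio of 224/365.25 = 0.61. Nothing in the SAP suggests this, and its 12-month wording and annualised output contradict it.
- *A third counting window in SAP Table 1.* The on-treatment wording there sits in a rationale column and contrasts the study with the prior year. It does not define a window.
- *Run-in exacerbations double-counted or misplaced.* SAP 8.1.2 takes the pre count at screening and the post count on study, so run-in events fall in neither. The pre-treatment label in SAP 10.4.1 only classifies records.

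**Conclusion.** The offset is wrong as written and should be corrected. It cannot be applied to the pre-mepolizumab records (Tables 2.18, 2.20, 2.21, 2.23, 2.24 and 2.26), although the intended 12 months is plain and no bias is expected from that gap. In the main analyses (Tables 2.18, 2.23 and 2.26) it pairs events counted to Week 32 with a time that ends with treatment. This overstates the on-study rate for any subject who stops treatment and remains under observation.

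The direction is against mepolizumab. The size depends on the number of such subjects, which the documents do not give. For 5-15% stopping with last dose at Week 4 to 20 and full follow-up, it is about 1-13% by crude person-time and about 1-25% under the negative binomial estimating equation with the assumed dispersion and rates. It is about 0% if the protocol's 4-week limit governs. These are illustrations under stated assumptions, not estimates of what will happen. A reader might infer that the study's main conclusion is at risk. It is not, because the primary ACQ-5 analysis does not use this model.

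**What to change.** Replace the offset sentence in SAP 8.1.2 with:

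*The offset is the logarithm of the time over which exacerbations are counted in each period: 12 months for the pre-mepolizumab record; for the post-mepolizumab record, first dose to the end of the exacerbation counting window for that analysis (for the on-treatment analyses, the end of the on-treatment phase in Section 10.4.1).*

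Then reconcile Protocol 7.3.2.4 with SAP 8.1.1 and 8.1.2 by stating which exacerbations after treatment discontinuation count in the main analysis, and record the offset change in SAP Table 1.

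The cost is two or three sentences before database freeze, with no new data collection if the protocol's window is followed. If the sponsor chooses to count to Week 32 after discontinuation, the protocol's collection window must be brought into line with that choice.

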#### **4.3. Type and Number of Subjects**

Approximately 155 subjects will be screened to achieve 120 treated with mepolizumab. Assuming a 15% withdrawal rate, this will result in approximately 100 evaluable subjects completing 32 weeks of mepolizumab treatment.

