### 9.2. Sample Size Considerations

#### 9.2.1. Sample Size Assumptions

The primary analysis will utilise within-subject changes from baseline. As this study is uncontrolled, the potential of a 'placebo effect' within the mepolizumab treated subjects will be considered. A meta-analysis of two previous severe asthma studies with mepolizumab (MEA115588 and MEA112997) estimated a change from baseline at Week 32 of -0.55 and -0.88 in the placebo and mepolizumab groups respectively, with mepolizumab presenting a benefit of -0.34 over placebo.

The following sample size estimates are based on a residual standard deviation of 0.96 units and are based upon the aforementioned meta-analysis. These estimates assume that 15% of subjects will prematurely withdraw from the study and therefore have missing

data at Week 32. This primary analysis will use the “missing at random” assumption for missing data.

With a sample size of 120 treated subjects, it is estimated that this study has over 90% power to detect a statistically significant improvement from baseline. Further it is estimated that a significant improvement over the ‘placebo effect’ of -0.55 from baseline in ACQ score will be observed at the two-sided 5% level of significance if the observed change from baseline is at least -0.74 units.

If the true change from baseline is -0.86 units, then the study has a probability of 90% of observing a change from baseline of at least -0.74 units and therefore the study has 90% power for declaring statistical significance over the ‘placebo effect’.

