2.4. Statistical Hypotheses

This study is designed to investigate whether subjects not optimally controlled on omalizumab can be effectively and safely switched to treatment with mepolizumab to improve asthma control. As there is no control arm in this study, comparisons in ACQ-5 score will be made to baseline. The first hypothesis to be tested will be for superiority of mepolizumab 100 mg SC treatment vs. baseline.

The potential of a ‘placebo effect’ within the mepolizumab treated subjects has been considered. In the protocol this was estimated as an improvement of -0.55 (SE: 0.05) from baseline in ACQ-5 score, based on the placebo effect observed in mepolizumab subjects from Phase 3 severe asthma studies (meta-analysis of double-blind studies MEA112997 and MEA115588). Improvements from baseline in ACQ-5 score will be assessed against this historical ‘placebo effect’. For further information regarding this historical ‘placebo effect’ please refer to Section 7.1.3.

Significance tests will be performed at the two-sided 5% alpha level (one-sided 2.5%).

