
 Adjusted means and the corresponding 95% confidence intervals will be presented by visit The estimated adjusted means will be presented using the observed marginal distributions of the sample covariates (OM option in LSMEANS statement). The Kenward and Roger method for approximating the denominator degrees of freedom and correcting for bias in the estimated variance-covariance of the fixed effects will be used (DDMF=KR). An unstructured covariance structure for the R matrix will be used by specifying 'type=UN' on the REPEATED line. Change from the baseline at each Visit X will be calculated by (Estimated Score at Visit X minus Estimated Score at Baseline) and the corresponding 95% confidence intervals. Adjusted means at each visit will also be presented. Plots of Least Squares (LS) mean change from baseline pre- and post bronchodilator FEV1 and 95% confidence intervals from the model will be generated at each visit.
On-treatment Phase
• See Primary Efficacy Statistical Analysis, Section 7.1.2

Other Statistical Analyses
Other Endpoint
• Subject rated response to therapy at Week 32
• Clinician rated response to therapy at Week 32
Results Presentation

 • The number and percentage of subjects in each response category will be presented for each visit. • The number of subjects with a missing responses at each visit will be presented in a separate category.
--

On-treatment Phase

 • An On-Treatment “de jure” analysis will also be performed which does not consider any data collected following treatment discontinuation (see On-Treatment definition within Section 10.4).

Other Statistical Analyses

Other Endpoint

 • Mean change from baseline in Treatment Satisfaction Questionnaire for Medication (TSQM-9)

Model Specification

 • The Mean Change at Week 32 will be tested to see if it is significantly different from zero using Wilcoxon signed-rank test

Model Checking & Diagnostics

 • Check for the extreme outliers by plotting the differences between TSQM-9 at Week 32 and Baseline

Model Results Presentation

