
 • Summary Statistics will be represented by study visit • The mean change at Week 32 will presented with the corresponding 95% CI and p-value in the table • The mean change at Week 32 will presented with the corresponding 95% CI in the figure
--

On-treatment Phase

 • An On-Treatment “de jure” analysis will also be performed which does not consider any data collected following treatment discontinuation (see On-Treatment definition within Section 10.4)
--

Other Statistical Analyses

Other Endpoint

 • Change from baseline in inflammatory biomarkers expression at week 32. The following biomarker parameters will be reported: CCL13, CCL17, ECP, EDN, Eotaxin1, Total IL-5, IL-13, MDC, Periostin, TSLP

Model Results Presentation

 • A log-transformation will be applied to each biomarker parameter prior to analysis. • Summary Statistics will be represented by study visit, including ratio to baseline • See Section 10.6.4 for further information regarding biomarker results below the lower limit of quantification

On-treatment Phase

 • An On-Treatment “de jure” analysis will also be performed which does not consider any data collected following treatment discontinuation (see On-Treatment definition within Section 10.4).

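### The Wilcoxon p-value planned for TSQM-9 does not test the mean change it is tabulated with, so the p-value and the 95% CI can contradict each other

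*SAP*

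**What the plan says.** TSQM-9 is one of the 'Other' endpoints (Protocol Section 3; SAP Section 2.2), defined as the mean change from baseline. SAP Section 8.1.2 gives the method: "The Mean Change at Week 32 will be tested to see if it is significantly different from zero using Wilcoxon signed-rank test". For presentation it says "The mean change at Week 32 will presented with the corresponding 95% CI and p-value in the table" and "The mean change at Week 32 will presented with the corresponding 95% CI in the figure". The only diagnostic is "Check for the extreme outliers by plotting the differences between TSQM-9 at Week 32 and Baseline". No other TSQM-9 test is named, so the p-value in the table must be the Wilcoxon one. The method for the interval is not stated, but by its wording it belongs to the mean. Neither a Hodges-Lehmann estimate nor a symmetry assumption appears. SAP Section 2.4 sets significance tests at the two-sided 5% level.

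The display lists do not match this. SAP Table 5 (Section 8.1.1) appears to mark TSQM-9 for summary displays only. Table 2.36 (Section 10.13.1.3) is titled a summary and covers three scales separately. The efficacy figure list (Section 10.13.1.4) contains no TSQM-9 figure.

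**The concern.** The sentence misdescribes its own test. A signed-rank test compares the rank sums of positive and negative changes. It asks whether the changes are symmetric about zero. If they are symmetric about some centre, that centre is also the mean, and the test serves as a test of the mean. If they are skewed, mean and pseudomedian differ, and the test can reject when the mean is zero or fail to reject when it is not.

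Nothing in the SAP secures symmetry: the score is bounded at 0 and 100, and an outlier plot does not check symmetry. What is at stake is the reading of one table. The report could call a mean change significant while its own CI covers zero, or the reverse, with no rule for which result to believe.

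**Working it through.** **Inputs.** Protocol Section 4.3: "Approximately 155 subjects will be screened to achieve 120 treated with mepolizumab". Protocol Section 9.2.1 assumes 15% withdraw, so n = 120 × 0.85 = 102. The plan gives no power, SD or effect for TSQM-9, so there is no TSQM-9 figure to reproduce. As a check on n, the ACQ-5 threshold is −0.55 − 1.96 × 0.96/√102 = −0.736, against −0.74 in the protocol. SAP Section 10.6.3 divides the Effectiveness and Convenience sums by 18, so one item point is 100/18 = 5.56. *Assumptions:* a t-based CI for the mean and, for the simulations, an SD of 20 points.

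**Step 1: can the two contradict each other?** Two constructed data sets, each with n = 102, show that they can. Changes take only the values +5.56 and −22.22 (one step up, four steps down; gap 27.78). With p the share of losers, SD = 27.78 × √[p(1 − p) × 102/101], and the CI is mean ± 1.984 × SD/√102. For Wilcoxon, the expected rank sum is 102 × 103/4 = 2626.5, and the variance is 102 × 103 × 205/24 − Σ(t³ − t)/48 = 89738.75 − tie term.

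*82 gain, 20 lose.*
- Mean = (82 × 5.56 − 20 × 22.22)/102 = +0.11. SD 11.08, SE 1.097, CI −2.07 to 2.29, which covers zero.
- Gains share the average rank 41.5, so W+ = 82 × 41.5 = 3403. Tie term = (551286 + 7980)/48 = 11651. z = (3403 − 2626.5)/√78087 = 2.78, p = 0.0055.
- Wilcoxon is significant, with a mean change of 0.1 on a 100-point scale.

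*72 gain, 30 lose.*
- Mean = (72 × 5.56 − 30 × 22.22)/102 = −2.61. SD 12.72, SE 1.259, CI −5.11 to −0.12, which excludes zero.
- W+ = 72 × 36.5 = 2628. Tie term = (373176 + 26970)/48 = 8336. z = (2628 − 2626.5)/√81402 = 0.005, p = 0.996.
- The contradiction now runs the other way.

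**Step 2: how often?** 20,000 simulated trials per row, n = 102, SD 20, two-sided 5%. 'Disagree' means that exactly one of Wilcoxon and the t-based CI declares a difference from zero.

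| Assumed shape of change | True mean | Wilcoxon rejects | t rejects | Disagree |
|---|---|---|---|---|
| Normal | 0 | 4.8% | 5.0% | 1.9% |
| Normal | 4 | 50.3% | 52.3% | 6.4% |
| Gamma, shape 4 | 0 | 13.2% | 5.1% | 11.2% |
| Exponential | 0 | 38.4% | 6.0% | 35.0% |
| Exponential, pseudomedian 0 | 3.2 | 5.6% | 33.0% | 33.4% |

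Rounding the normal changes with mean 4 to the 5.56-point steps gives 5.7%, so coarseness alone adds nothing.

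**Step 3: dependence on shape and effect.** Other choices of shape, direction of skew and mean gave about 1-6% for symmetric changes. Skewed changes with a mean of 0 to 4 points gave roughly 8-37% in one set of shapes and 11-46% in another that included the exponential skewed either way. At 8 points the skewed shapes gave 3-18%, at 10 points at most about 1%, and at 12 points near 0%. The reason is power. The SE is 20/√102 = 1.98, so a mean of 4 is 2.0 SE, right at the threshold. A mean of 12 is 6.1 SE, where both methods reject almost always.

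**The case against.** A rank test is a recognised choice for paired scores built from ordinal items, and it fits the SAP's concern with outliers. A bounded, coarse scale does not by itself break it. If baseline and Week 32 scores are exchangeable, their differences are symmetric about zero whatever the ceiling or ties. In simulated ceiling-skewed scores of that kind (n = 102), Wilcoxon rejected 4.7-5.1% of the time, the t-test 4.6-4.8%, and they disagreed in 1.7-2.0%. Nor are all three scales equally coarse. In Overall Satisfaction, Items 7 and 8 move by 100/12 = 8.33, but the recoded Item 9 moves by 8.33 × 5/6 = 6.94, so attainable scores lie on a finer grid of about 1.39. The CI for the mean is reported in any case, and the endpoint carries no power claim or decision rule.

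All of this stands, and it limits the point. A reader might infer that the Wilcoxon test is invalid here, or that a quarter or a third of such trials would give a false result. The documents support neither. They give no information on the shape of TSQM-9 change, and the higher rates arise only when a strong skew is assumed together with a small or moderate mean change. A reader might also picture p-value and CI on one row; the SAP says only that both are in the table, and the shells are separate documents (Section 10.14). What the objection does not remove is that the plan calls a signed-rank test a test of the mean and pairs its p-value with the mean.

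**Conclusion.** The point holds as a mismatch between test and estimate. The SAP's description is correct only under symmetry, which it neither assumes nor checks, and the Step 1 examples show contradiction in both directions at the planned size. The frequency in this trial cannot be stated. The rates above rest on an assumed SD of 20, assumed shapes, 102 subjects with Week 32 data and a t-based CI; they show a range and predict nothing. If the change turns out large (about 12 points under these assumptions) or symmetric, the mismatch will hardly show. It is a minor reporting matter on an 'Other' endpoint, with no bearing on the ACQ-5 result or the sample size. The inconsistency between Section 8.1.2 and the display lists needs no assumption about the data.

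**What to change.** In SAP Section 8.1.2, make the estimate, CI and p-value refer to one quantity, and say that this applies to each of the Effectiveness, Convenience and Overall Satisfaction scales. Either option works:

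- Keep the Wilcoxon test, describe it as a test of location under symmetry, and report the Hodges-Lehmann estimate with the 95% CI obtained from the same test. Keep the mean as a descriptive summary.
- Keep the mean and its CI, and take the p-value from the matching one-sample t-test on the changes. With about 100 subjects this is reasonable.

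With either choice, estimate and test match and disagreement is 0% by construction. The choice between them is a preference; the consistency is not. State the CI method as well.

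Then reconcile the displays: mark a statistical analysis for TSQM-9 in Table 5 and retitle Table 2.36, or drop the test. Add the promised figure to Section 10.13.1.4, or delete it from Section 8.1.2. The cost is one or two SAP sentences, at most one extra table column, and an edit to the display lists, with no change to data collection.
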